APPENDIX A: Informed Consent

APPENDIX B: Case Report Forms

APPENDIX C: Declaration of Helsinki

A Prospective, Multi Center Pilot Study Evaluating Plaque Photoablation Using the RA-308 Excimer Laser in Subjects with Symptomatic Infrainguinal Lower Extremity Vascular Disease

SYNOPSIS

- Study Objective** To evaluate the safety and efficacy of the RA-308 Excimer Laser System and DABRA Catheter for treating subjects with symptomatic infrainguinal lower extremity vascular disease with chronic total occlusions that cannot be crossed with standard guide wires.
- Study Device** The RA-308 Excimer Laser System and DABRA 101 Catheter consists of a 308 nanometer wavelength Excimer laser and a fluid filled optical catheter.
- Study Design** A multi-center, prospective, non-randomized, open-label study. The study will be conducted at a minimum of two sites.
- Sample Size** Up to 50 male and female subjects will be enrolled.
- Outcome Measures** Procedural success, defined as crossing the target lesion based on angiographic analysis at the time of the procedure. Crossing the target lesion is defined as successfully placing any endovascular device distal to the occlusion.
- No device related major adverse events.

STUDY POPULATION

Inclusion Criteria

Subjects must satisfy the following criteria before entering the study:

- Signed informed consent obtained.
- Symptomatic infrainguinal lower extremity vascular disease (Rutherford category 3, 4, 5 or 6), stable for at least 2 weeks prior to study inclusion.
- Lesions in the superficial femoral artery (SFA), popliteal, infrapopliteal or tibial arteries
- At least one angiographically identifiable infrageniculate artery
- Patients must be poor surgical candidates, indicated by at least one of the following conditions:
 - Absence of venous autologous grafts (that is, lack of a suitable vein to use for bypass)
 - Poor (diffusely diseased or ≤ 1 mm diameter) or no distal vessels available for graft anastomosis

- High risk of surgical mortality, evidenced by American Society of Anesthesiologists Physical Class 4 or higher
- Have a lesion that is a chronic total occlusion that cannot be crossed with a standard guidewire. NOTE: This can only be determined at the time of the procedure.

Exclusion Criteria

Potential subjects who meet any of the following criteria will be excluded from participating in the study:

- Age below 18 years
- Pregnancy, or plan to become pregnant
- Participation in another cardiovascular or peripheral vascular IDE study
- Myocardial infarction (MI) in prior month
- Stents at treatment site
- Disorders or allergies precluding use of radiographic contrast
- Renal insufficiency severe enough to contraindicate use of radiographic contrast
- Contraindication to treatment with anticoagulants
- Untreated ipsilateral iliac stenosis >70%
- Inability or unwillingness of the patient to comply with intended examinations.
- Unavailability of required procedural or imaging equipment
- Lesion located in a graft
- Hemodynamically significant arrhythmia or left ventricular ejection fraction <20%
- Life expectancy less than 6 months
- Necrosis necessitating major amputation
- Unwillingness of the patient to be anti-coagulated

Time and Events Schedule

Event	Screening (Visit 1)	Procedure (Visit 2)	Follow-Up
		Day 0	≥30 Days
Demographics and Medical History Review	X		
Ankle-Brachial Index (ABI)	X		As needed
Rutherford Classification	X		
Angiography		X	
Crossing Procedure		X	
Device-Related Safety Data		As needed	As needed
Doppler Ultrasound			As needed

1.0 INTRODUCTION

1.1 Background

The distribution of Peripheral Artery Disease (PAD), including Chronic Total Occlusions (CTOs), varies with multiple factors, such as age and the presence of cardiovascular risk factors. Aortoiliac disease is associated with young age, females, and current smokers. Femoropopliteal involvement in occlusive PAD is extremely common and, in one series, was present in 80% of symptomatic patients undergoing angiography. The predilection of disease in this segment may be due to its conduit-like nature, with no or few major branches, and torsion or stretching resulting from limb movement. These characteristics may cause relatively more damage of the vaso vasorum and endothelium than other limb segments, leading to accelerated atherosclerosis. Additionally, the flow characteristics following the development of a stenosis may promote long occlusions. Infrapopliteal disease is associated with diabetes mellitus, and diffuse and occlusive disease is common. Despite the complex nature of infrapopliteal disease, endovascular techniques have acceptable limb salvage rates. This approach, therefore, may be increasingly used for CTOs in patients with limited surgical options, due to co-morbidities or lack of bypass conduits or target vessels. Overall, CTOs are more the norm than the exception in PAD. The decision to attempt percutaneous revascularization of CTOs depends on many factors, such as severity of symptoms, and lesion characteristics, including location, calcification and length, and operator experience and institutional availability of the specialized devices.

From 1975-1979 many scientists and institutions worked on the initial development of a family of gas lasers known as the "excimer." Those pioneers were with institutions including Lumonics, Lambda Physik, Avco, and Caltech. The development was initiated in part because of the short wavelength of this type of light source. Monochromatic short wavelength sources were thought to have a variety of commercial and military applications. The name excimer is a contraction of "Excited Dimer," a description of a diatomic molecule in which the component atoms are bound in the excited state, but not in the ground state. The important gas molecules are rare gas halides including argon fluoride, krypton fluoride, and xenon chloride.

The ultraviolet light from an excimer laser is well absorbed by biological matter and organic compounds. Rather than burning or cutting material, the excimer laser adds enough energy to disrupt the molecular bonds of the surface tissue, which effectively disintegrates in a tightly controlled manner through ablation rather than burning. Thus excimer lasers have the useful property that they can remove exceptionally fine layers of surface material with almost no heating or change to the remainder of the material which is left intact. These properties make excimer lasers well suited to precision micromachining organic material, or delicate surgeries such as eye surgery. At lower energy densities, the laser may also be used for dermatological disorder treatment.

Excimer laser light is typically absorbed within the first billionth of a meter (nanometer) of tissue. In the early 1980s, researchers at IBM's T. J. Watson Research Center observed the effect of the ultraviolet excimer laser on biological materials. They found that the laser made clean precise cuts that would be ideal for delicate surgeries. Subsequent work introduced the excimer laser for use in angioplasty or atherectomy, destroying blockages in arteries using molecular ablation. Xenon chloride excimer lasers, having a wavelength of

308nm, can also treat a variety of dermatological conditions including psoriasis, vitiligo, atopic dermatitis, and leukoderma.

In the late 1980s, 308nm excimer laser atherectomy was developed as an alternative method of percutaneous angioplasty, with the objective of reducing the high rate of restenosis associated with other angioplasty or stenting techniques. Excimer laser atherectomy is a procedure that utilizes an intravascular catheter system to deliver high-energy pulsed laser light to atherosclerotic lesions, or plaque, that are causing stenosis or occlusion of native arteries, or intra-arterial stents, while producing relatively little thermal damage to the vessel wall. The pulses vaporize thin sections of tissue without causing significant damage to surrounding tissue. It is thought that reduction of plaque using laser ablation could be more effective in enlarging the vessel lumen than balloon angioplasty alone. Early data from large observational registry studies published in the early 1990s provided evidence of the safety of the procedure. By 1994, Advanced Interventional Systems (AIS) had commercialized a system and gained FDA approval for the procedure. Later in the decade AIS merged with Spectranetics, Inc., which had developed an excimer for treating peripherals. There are approximately 1,000 Spectranetics lasers placed today, and thousands of excimer laser endovascular procedures are performed each year.

The Ra Medical team, which includes members of the Spectranetics and AIS development teams, began developing the RA-308 Excimer Laser System and DABRA Catheter for crossing lesions in 2006, after the successful launch of the PHAROS EX-308 excimer laser phototherapy system.

1.2 Alternative Treatments and Methods

Patients that have agreed to participate in the study and meet the inclusion criteria and have signed the informed consent form and present on the day of treatment for the endovascular diagnostic procedure will be considered for the study. It is at this point when it will be determined that the patient meets all of the inclusion criteria. If the patient's lesion can be crossed with a guide wire or if the physician feels that other options are more appropriate for the patient, the patient will be treated with the laser catheter and not be included in the study.

There are several commercially available CTO crossing methods and atherectomy systems on the market today. These include standard guide wire manipulation. Standard guide wire recanalization should initially be attempted, even for long, occlusive lesions. Although the inability to remain intraluminal or re-enter the true lumen distally are the main reasons for failure of this technique, there is still a relatively high chance of success. For aortoiliac lesions, an ipsilateral retrograde femoral approach is usually the simplest, but an alternative approach from contra lateral femoral or brachial access may be needed. For superficial femoral artery (SFA) lesions, a contra lateral femoral approach with a crossover sheath is usually needed, but for more distal lesions, such as infrapopliteal, an ante grade femoral approach may be preferable, so that device torquability and push ability is optimized.

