1.5 Risk Analysis

We believe that the procedure does not pose a significant risk to the patient. The patients are likely candidates for amputation. In addition, the procedure does not pose additional risk to the patient because of the following:

- The endovascular procedure will occur anyway, regardless of whether or not the laser is used. This endovascular procedure is used to help diagnose the precise nature of the disease, the location of any stenosis, and treatment will be initiated with common endovascular tools, such as guidewires and balloons. The DABRA laser catheter will be attempted only after these tools fail or if the physician determines that there is no other option.
- The catheter does not present a potential for serious risk to the health, safety, or welfare of the subject, because they already have a high probability of amputation. In addition, the potential adverse events related to the DABRA catheter have low risk to these patients. Perforation is easily mitigated and repaired with a tamponade technique, and embolism or debris from any of these procedures is likely to be filtered downstream by the narrowing of the vasculature.
- The catheter is not implanted, and is not of substantial importance in treating the disease. It only crosses the lesion to allow therapeutic treatment. It is a small part of a much more complicated procedure. The energy delivered by the DABRA catheter is orders of magnitude less than other technologies, including mechanical, barometric, radiofrequency, and ultrasonic or sonic.
- All endovascular interventionalists have the skill and training to use this device safely. Excimer lasers have been used for over 20 years, and their operation is no more difficult than using a stand alone guide wire. The only difference is depressing the footswitch.

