3.0 STUDY POPULATION

3.1 General Considerations

Subjects will undergo baseline evaluation to determine eligibility for the study. Subjects who do not meet the entry criteria are considered screening failures. Case report forms do not need to be completed for screening failures; however, a record for each patient screened and the reason for screening failure must be indicated in the screening log.

The investigator and/or designated study personnel are responsible for screening all potential candidates and selecting those who are appropriate study candidates as defined by the following inclusion and exclusion criteria.

Signed informed consent will be obtained from the patient before any specific study procedures are undertaken. The patient will sign one original informed consent and a copy will be provided to them. The study requirements should be discussed with the patient with ample time provided for the consent review. All required parties (e.g., patient, witness, investigator or designee) should sign and date on the same consent as the patient.

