3.2 Inclusion Criteria

Subjects must satisfy the following criteria before entering the study:

- Signed informed consent obtained.
- Symptomatic infrainguinal lower extremity occlusive vascular disease (Rutherford category 3, 4, 5 or 6), stable for at least 2 weeks prior to study inclusion.
- Lesions in the superficial femoral artery (SFA), popliteal, or infrapopliteal arteries
- At least one angiographically identifiable infrageniculate artery
- Patients must be poor surgical candidates, indicated by at least one of the following conditions:
 - Absence of venous autologous grafts (that is, lack of a suitable vein to use for bypass)
 - Poor (diffusely diseased or ≤ 1 mm diameter) or no distal vessels available for graft anastomosis
 - High risk of surgical mortality, evidenced by American Society of Anesthesiologists Physical Class 4 or higher
- Have a lesion that is a chronic total occlusion that cannot be crossed with a standard guidewire. NOTE: This can only be determined at the time of the procedure.

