4.2 Excimer Laser for Use in Plaque Photoablation

Refer to the device Instructions for Use for a thorough description of the procedure.

Procedure Description

The excimer laser crossing procedure is performed in the Catheter Laboratory using standard endovascular techniques. Following introduction to the vascular system and diagnosis using fluoroscopy, including determining that a standard guidewire cannot cross the lesion, the following general guidelines are followed:

1. Insert a commercial guide wire to the blockage.
2. Pass an appropriate guiding catheter (support catheter) over the wire to the lesion. (Steps 1 & 2 can be reversed depending on physician choice.)
3. Remove the guide wire if one fails to cross the CTO or if, at the physician's discretion, angiographic factors determine that a guide wire should not be used because of the presence of a rounded or eccentric stump might bias the guide to a subintimal route, or other complicating factor.
4. Save the initial guide wire and insert the laser catheter and perform a stepwise crossing of the lesion.
5. Cross the CTO with the laser catheter following the step-by-step procedure in the instructions for use.
6. Exchange the laser catheter with the previous wire or another wire.
7. Remove the guide catheter leaving the guide wire in place and, at the physician's discretion, insert other endovascular devices to enhance blood flow.

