5.3 Procedure

The following information will be collected for study subjects:

- Pre-laser treatment stenotic assessment using angiography
- Laser treatment procedure time
- Post-laser treatment stenotic assessment using angiography
- Adjunctive procedures, if any, as recommended by the physician
- The duration of lasing
- Device related safety data

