11.0 MONITORING RESPONSIBILITIES

Ra Medical Systems, Inc. will serve as the sponsor of this clinical investigation. It is the responsibility of Ra Medical as the sponsor of the study to ensure proper monitoring of the investigation and to see that all the clinical requirements are met.

The procedural success determination is crossing the lesion that could not be crossed with a standard guide wire, and therefore not subject to bias. The procedural success is determined using fluoroscopic angiography and is not subject to bias, interpretation, or quantification,

because the lesion is either crossed or not crossed. Because of these facts, third party involvement in determining procedural success would have no added value and provide no additional verification. The placebo effect also need not be considered. It is not possible for the patient to affect the blockage during the procedure.

All information and data sent to Ra Medical concerning subjects and their participation in this investigation will be considered confidential. Only authorized Ra Medical personnel, Ra Medical representatives, and regulatory agencies will have access to these confidential files. All data used in the analyses and reporting of this investigation will be coded without identifiable reference to the subject.

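### Section 1.2, read literally, gives the laser to patients whose lesion a guide wire can cross and leaves them out of the study, contradicting section 1.5 and the lead-in to section 4.2

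*Combined protocol and SAP*

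**What the plan says.** Section 1.2 describes consented patients who arrive for the endovascular diagnostic procedure and have their eligibility settled there. For those whose lesion a wire can cross, or for whom the physician thinks another option is better, it concludes that "the patient will be treated with the laser catheter and not be included in the study".

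Other parts of the protocol describe laser use differently:

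- Section 1.5, after naming guidewires and balloons as the usual tools: "The DABRA laser catheter will be attempted only after these tools fail or if the physician determines that there is no other option". This stands in the list introduced by "the procedure does not pose additional risk to the patient because of the following".
- Section 4.2, in the lead-in to the numbered steps, places diagnosis before the laser, "including determining that a standard guidewire cannot cross the lesion".
- Section 11.0 describes procedural success as "crossing the lesion that could not be crossed with a standard guide wire".
- Section 3.2, and the same list in the Synopsis, make it an entry criterion: "Have a lesion that is a chronic total occlusion that cannot be crossed with a standard guidewire".

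On data collection, section 3.1 treats people who fail the entry criteria as screening failures and says "Case report forms do not need to be completed for screening failures", although the screening log must show the reason. Section 5.3 opens its list, which includes device-related safety data, with "The following information will be collected for study subjects". Section 6.6.1 tabulates adverse events by subject, and section 8.1 defines them for a subject of the investigation who received the device.

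**The concern.** The protocol gives two incompatible answers to one question: does a patient whose lesion a wire can cross receive the laser catheter? Section 1.2 says yes, outside the study. Section 1.5 and the lead-in to 4.2 say that laser use follows a failed crossing or the absence of another option.

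Two things are at stake. The first is exposure to an investigational device, together with the reasoning that supports it: 1.5 counts restricted use of the laser among its grounds for saying that the procedure adds no risk, and 1.2 as written removes that restriction. The second is the safety record. The safety outcome in 2.2.1 is the absence of any device-related major adverse event, so it matters whether an event in a lasered person would be captured. Anyone treated under the literal wording of 1.2 would have received the device without being a study subject.

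**Working it through.** The point is textual, so the main check sets the passages side by side.

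**Step 1. Compare the rules for a lesion that a wire can cross.**

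| Section | Laser used? | In the study? |
|---|---|---|
| 1.2 | Yes | No |
| 1.5 | Only if tools fail or no other option exists | Not addressed |
| 4.2 lead-in | Laser steps follow a finding that the wire cannot cross | Not addressed |
| Synopsis and 3.2 | Not addressed | No |

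Section 1.2 agrees with 3.2 on enrolment. It conflicts with 1.5 and 4.2 on exposure.

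**Step 2. Look for a provision that removes the conflict.** Two passages allow the laser without a failed wire attempt. The objective in 2.2 adds lesions where the operator expects an attempt to end in a subintimal path or a perforation. Step 3 of 4.2 lets the physician set the wire aside for angiographic reasons or another complicating factor. Neither covers a lesion that a wire can cross. They do show that the rule on laser use already differs between sections, so both belong in the reconciliation.

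**Step 3. Trace the data for a person treated under 1.2 as written.**

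- The person fails the criterion in 3.2 and is therefore a screening failure under 3.1: a log entry, with no CRF required.
- The procedure and safety items in 5.3 are listed for study subjects.
- The tables in 6.6.1 and the definition in 8.1 refer to subjects. They do not say whether a lasered screening failure counts as one.
- Some trace would remain: the screening log (3.1), the non-compliance log, which names unmet entry criteria (9.3), and device accountability (10.0). None of these is an adverse-event record.

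The safety data therefore have no clear place for such a person, although nothing forbids recording the event.

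**Step 4. Check whether the primary test is touched.** Inputs from 6.1, 6.2 and 6.5: null rate 0.65, assumed true rate 0.97, one-sided exact binomial test at 0.025, with success declared at 13 or more of 14, or 40 or more of 50.

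- For n = 14, P(X ≥ 13) = 14·p^13·(1 − p) + p^14.
- At p = 0.97 this is 0.2827 + 0.6528 = 0.9355, matching the stated 94%.
- At p = 0.65 it is 0.0181 + 0.0024 = 0.0205, below 0.025.
- For n = 50 with 40 or more, the exact binomial tail is above 0.9999 at 0.97 (stated 99.99%) and 0.0160 at 0.65.

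The sentence in 1.2 enters none of these calculations, because the people it describes are not enrolled.

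**The case against.** The strongest reply is that this is a slip of the pen. Read literally, the sentence sends a patient to the laser because another option is more appropriate, which makes little sense. The next paragraph of 1.2 says that wire recanalization should be tried first. Section 1.2 is introductory, while eligibility is set in 3.2 and the procedure in 4.2. If the sentence is corrected so that nobody outside the study is lasered, the data gap it creates closes. All of this is fair, and the slip is the likeliest explanation. The contradiction nevertheless remains in current text, in a rule meant to be applied on the day of treatment, and a reader should not have to guess which section governs.

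It can also be said that such people have consented, that 3.1 itself calls screening failures subjects, and that 6.6.1 and 8.1 might therefore include them. That is possible, so the gap is one of unclear wording rather than demonstrated exclusion. The consent and CRF pages are not available here and cannot be judged.

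Three stronger readings are tempting, and the documents support none of them:

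- **That the safety estimate is biased by a known amount.** One might compare 0 events in 50, with a one-sided 95% exact upper bound of 1 − 0.05^(1/50) = 5.8%, with 1 event in 51 to 60, where the bound (the 0.95 quantile of a beta distribution with parameters x + 1 and n − x) is 9.0% to 7.7%. That rise comes wholly from the assumed event. With no event, counting the extra people lowers the bound to between 5.7% (n = 51) and 4.9% (n = 60). The protocol gives neither the number of people nor an event, and it sets no safety bound.
- **That failures could be removed from the primary denominator.** Under 1.2, exclusion turns on whether a wire can cross or on the physician's preference among options, not on whether the laser succeeded.
- **That this study supplies nearly all the relevant safety experience.** Section 1.4 reports three earlier patients, but only for this device. Section 1.1 describes registry evidence and routine use of 308 nm excimer atherectomy more broadly.

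**Conclusion.** The contradiction holds. Section 1.2 as written cannot be squared with 1.5 or with the lead-in to 4.2, and the discretionary routes in 2.2 and in step 3 of 4.2 do not rescue it. It is probably a drafting error, but it is more than clerical, because it bears on who receives the study device and on a stated premise of the risk argument.

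The consequence for safety data is conditional. It arises only if the sentence is followed literally or someone is lasered without being enrolled. In that case no CRF is required, and the placement of the person's events is unclear, although other logs would leave some record. Sample size, power and type I error are unaffected. The size of any safety effect cannot be computed, because the documents do not say how many people might be exposed. The conclusion rests on the visible text alone, and no view is taken here on which clinical rule is right.

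**What to change.** Reconcile section 1.2 with the Synopsis criteria, 1.5, the objective in 2.2, the criteria in 3.2, and 4.2 including step 3, so that all state one rule on who receives the laser. The sponsor and investigators decide that rule.

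Add a sentence to 6.6.1: if the reconciled text allows, or an error leads to, laser use in anyone not enrolled, that person has a CRF, and their adverse events are reported separately from those of enrolled subjects. Align 3.1 so that its CRF exemption does not extend to a screening failure in whom the laser was used.

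The primary analysis needs no change on this account. The cost is a few sentences, plus a CRF for any such person, with no extra patients or procedures.
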